Visit	1	2 ^a	3	4	5	6 ^b (EOT)	7 (EOS)	Visit window: ± 3 days for Visits 3, 4, 5, 6, and 7.
DLQI		X	X	X	X	X	X	Entered by participant during site visit on a tablet provided to the site.
HADS		X			X	X	X	
EQ-5D-5L		X			X	X	X	
PGIS	X	X	X	X	X	X		
PGIC			X	X	X	X		
Missed school/work days (baseline version)		X						
Missed school/work days (postbaseline version)					X	X	X	
Modified PAS (screening- baseline version)	X	X						Investigator's assessment to be entered on a tablet provided to the site.
Modified PAS (follow-up version)			X	X	X	X	X	
IGA PN-A and IGA PN-S		X	X	X	X	X	X	
Optional photography (substudy)		X	X	X	X	X	X	

a All assessments at Visit 2 (Day 1) are to be conducted pre-IMP dose with the exception of the assessment of local tolerability of SC injections.

b Participants who discontinue the study treatment prematurely (prior to completing the 24-week treatment period) will perform the EOT assessments at the time of discontinuation to assure a complete clinical assessment in close temporal proximity to the premature termination of study treatment. In addition, to allow assessment of participant outcomes over the stipulated study period, participants will be asked and encouraged to complete all remaining study visits and participate in all assessments according to the visit schedule.

c In case of results showing HBs Ag (negative) and HBc Ab (positive), an HBV DNA testing will be performed and should be confirmed negative prior to randomization. In case of results showing HCV Ab (positive), HCV RNA testing will be performed and should be confirmed negative prior to randomization.

d Assessments/procedures should be conducted in the following order: PRO, investigator assessments, safety and laboratory assessments (including sample collection for ADA, PK, biomarker, and optional DNA and RNA), and administration of IMP.

e Refer to [Section 10.2](#) and central lab manual for collection details.

f PK and ADA samples to be collected prior to the administration of the drug. In the event of any SAE, any AE of severe injection site reaction lasting longer than 24 hours, or any AESI of anaphylactic reaction or systemic allergic reaction that is related to IMP and require treatment, PK and ADA samples will be collected at or near the onset of the event for any additional analysis if required or for archival purposes. Samples for ADA will only be collected for analysis in the event of any SAE for participants from China sites.

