10.10 APPENDIX 10: COUNTRY-SPECIFIC REQUIREMENTS

China:

1. Urine pregnancy test can be done at local lab according to the local requirement at Week 16, Week 20, Week 28, and Week 32.
2. Scheduled PK and ADA samples will not be collected.

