3 ANALYSIS POPULATIONS

The following populations for analyses are defined:

Table 4 - Populations for analyses

Population	Description
Screened	All participants who sign the ICF.
Randomized	The randomized population includes all participants with a treatment kit number allocated and recorded in the interactive response technology (IRT) database, and regardless of whether the treatment kit was used or not. Participants treated without being randomized will not be considered randomized and will not be included in any efficacy population.
Intent-to-treat (ITT)	All randomized participants analyzed according to the intervention group allocated by randomization regardless if treatment kit is used or not
Efficacy	The ITT population
Safety	All participants randomly assigned to study intervention and who take at least 1 dose of study intervention. Participants will be analyzed according to the intervention they actually received. Randomized participants for whom it is unclear whether they took the study medication will be included in the safety population as randomized. For participants who accidentally receive different treatment from the planned, the actual intervention allocation for as-treated analysis will be the dupilumab group. The PD analyses will be performed on the safety population.
Pharmacokinetic (PK)	The PK population includes all participants in the safety population with at least one non-missing result for functional dupilumab concentration in serum after first dose of the study treatment. Participants will be analyzed according to the intervention actually received.
Antidrug antibody (ADA)	ADA population includes all participants in the safety population who have at least one non-missing ADA result after first dose of the study treatment. Participants will be analyzed according to the intervention actually received.

ADA: antidrug antibody; ICF: informed consent form; ITT: intent to treat; PD: pharmacodynamics; PK: pharmacokinetic.

Participants exposed to study intervention before or without being randomized will not be considered randomized and will not be included in any analysis population. The safety experience of these participants will be reported separately.

Randomized participants for whom it is unclear whether they took the study intervention will be considered as exposed and will be included in the safety population as randomized.

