4.8.2 Immunogenicity analyses

Anti-drug antibody (ADA) status to dupilumab (negative or titer value, if positive in the ADA assay) at Visit 2 (Day 1), Week 12, Week 24/EOT and follow up at Week 36 will be provided. The neutralizing antibody status for ADA positive samples will be provided.

Incidence will be provided for the following ADA response categories:

Pre-existing immunoreactivity is defined as:

An ADA positive response in the assay at baseline with all post first dose ADA results negative, OR an ADA positive response at baseline with all post first dose ADA responses less than 4-fold over baseline titer levels.

Treatment-emergent ADA response is defined as:

A positive response in the ADA assay post first dose, when baseline results are negative or missing.

Treatment-emergent ADA responses are further classified as Persistent, Indeterminate or Transient

- A) Persistent Response- defined as a treatment-emergent ADA response with two or more consecutive ADA positive sampling time points, separated by greater than ($>$) 12-week period (84 days), with no ADA negative samples in between.
- B) Indeterminate Response- defined as a treatment-emergent response with only the last collected sample positive in the ADA assay
- C) Transient Response - defined as a treatment-emergent response that is not considered persistent OR indeterminate

Treatment-boosted response is defined as:

An ADA positive response in the assay post first dose that is greater-than or equal to 4-fold over baseline titer levels, when baseline results are positive.

Titer values (Titer value category)

- Low (Titer < 1000)
- Moderate ($1000 \leq \text{Titer} \leq 10\,000$)
- High ($\text{Titer} > 10\,000$)

The following summary will be provided based on ADA population:

- Number (%) of participants with pre-existing immunoreactivity
- Number (%) of participants with treatment-emergent ADA
- The summary statistics (including number, median, Q1, Q3, minimum and maximum) of the peak post-baseline titer for participants with treatment-emergent ADA, and participants with persistent, indeterminate and transient ADA response
- Number (%) of participant with transient treatment-emergent ADA
- Number (%) of participants with persistent treatment-emergent ADA
- Number (%) of participants with indeterminate treatment-emergent ADA
- Number (%) of participants with treatment-boosted ADA

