- The summary statistics (including number, median, Q1, Q3, minimum and maximum) of the peak post-baseline titer for participants with treatment-boosted ADA
- The summary statistics (including number, mean, SD, median, Q1, Q3, minimum and maximum) of the ratio of peak post-baseline titer to baseline titer for participants with treatment-boosted ADA
- Listing of ADA peak titer levels and neutralizing antibody status
- Number (%) of participants with neutralizing antibody status.

Kinetics of treatment-emergent ADA response

Number (%) of participants with treatment-emergent ADA positive response at each visit will be summarized, including titer categories (lower, moderate, and high titer), by each intervention group.

A plot of percentage of participants with treatment-emergent ADA positive response at each visit will be provided by each intervention group.

Association of Immunogenicity with Exposure, Safety and Efficacy

The safety and efficacy analyses mentioned below will be conducted using the following categories:

- ADA positive participants: Participants with treatment-emergent or treatment-boosted response.
- ADA negative participants: Participants with pre-existing immunoreactivity or negative in the ADA assay at all time points.

Association of ADA with PK

Associations between ADA variables (eg, ADA peak titers, neutralizing antibody status, treatment-emergent, persistent, indeterminate and transient response, treatment-boosted) and concentration of dupilumab in serum may be explored for each dupilumab dose group. A plot of

concentration of functional dupilumab versus visit will be provided by ADA classifications for the dupilumab dose group. Individual participant plots of dupilumab concentration according to ADA status will be provided to assess the impact of ADA on PK.

Association of ADA with clinical efficacy endpoints

Associations between the ADA variables (eg, ADA peak titers, neutralizing antibody status, treatment-emergent, persistent and treatment-boosted) and the primary efficacy endpoint may be explored for the dupilumab dosed group.

Association of ADA with clinical safety endpoints

Association of safety versus ADA status may be analyzed in the ADA population. The safety assessment may focus on the following events:

- Severe injection site reactions last longer than 24 hours or serious injection site reactions
- Hypersensitivity reactions (SMQ (20000214) hypersensitivity narrow search confirmed by medical review)

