		To reflect that the primary endpoint timepoint is Week 24.	To maintain consistency in language with the change in the primary endpoint.
		To update Table 6 to reflect that the primary endpoint is assessed at Week 24.	To maintain consistency in language with the change in the primary endpoint.
		To remove the possibility of re-evaluating the timing of the primary database lock of EFC16459 based on the observed treatment effect size in EFC16460, that was added per Amendment 02. And to consequently remove the 2 populations (ITT-Week 12 and ITT-Week 24) that were added per Amendment 02.	Amended protocol 02 was submitted in few countries but was withdrawn following a Health Authority feedback and was not implemented in any country.
		Subsection 10.12.2 was added and the overall rationale and table with summary of changes for Amended protocol 02 were moved from the cover page to this section.	This is aligned with Sanofi procedures.

5.3 APPENDIX 3 DEMOGRAPHICS AND BASELINE CHARACTERISTICS, PRIOR OR CONCOMITANT MEDICATIONS/PROCEDURES

Demographics, baseline characteristics, medical surgical history

The following demographics and baseline characteristics, medical and surgical history and disease characteristics at baseline will be summarized using descriptive statistics in the randomized population.

Demographic variables are

- Age in years (quantitative and qualitative variable: 18-<40, 40-<65, 65-<75, and ≥ 75 years),
- Gender (Male, Female),
- Race (White, Black or African American, Asian, American Indian or Alaska Native, Native Hawaiian or other Pacific Island, unknown),
- Ethnicity (Hispanic or Latino, Not Hispanic or Latino, Unknown),
- Region (Asia: Japan, China, South Korea; East Europe: Russia; Latin America: Argentina, Mexico; Western Countries: USA, France),

- Territory (North America: USA; European Union: France; Rest of World: Russia, Japan, China, South Korea, Argentina, Mexico),
- Weight in kg (quantitative and qualitative variable: (<60, \geq 60- <90, \geq 90 kg),
- BMI in kg/m² (quantitative and qualitative variable: (<25, \geq 25- <30, \geq 30 kg/m²).

Baseline safety and efficacy parameters (apart from those listed above) will be presented along with the safety and efficacy summaries.

Medical (or surgical) history includes all the relevant medical (or surgical) history during the lifetime of the participant.

This information will be coded using the version of MedDRA currently in effect at Sanofi at the time of database lock.

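### Participants at China sites can enter the ADA population only through an SAE and always without a baseline sample, so the ADA denominator should rest on scheduled samples

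*SAP*

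**What the plan says.** The SAP (section 3, Table 4) defines the population in these words: "ADA population includes all participants in the safety population who have at least one non-missing ADA result after first dose of the study treatment". Protocol section 9.3, Table 5, has the same rule. Neither limits it by sample type or country.

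China is a participating country; the region list in SAP Appendix 3 reads "Asia: Japan, China, South Korea". For China, Protocol section 10.10 states: "Scheduled PK and ADA samples will not be collected". Footnote f of the schedule of activities (Protocol 1.3) adds: "Samples for ADA will only be collected for analysis in the event of any SAE for participants from China sites".

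At other sites the planned ADA time points are "at Visit 2 (Day 1), Week 12, Week 24/EOT and follow up at Week 36 will be provided" (SAP 4.8.2), that is, three scheduled post-dose samples. Footnote f also asks for extra ADA samples after SAEs, long-lasting severe injection site reactions and certain allergic reactions, "at or near the onset of the event for any additional analysis if required or for archival purposes".

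SAP 4.8.2 defines a treatment-emergent response as "A positive response in the ADA assay post first dose, when baseline results are negative or missing". On the link to safety it says: "Association of safety versus ADA status may be analyzed in the ADA population".

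**The concern.** Incidence of treatment-emergent ADA is a listed secondary endpoint. Followed as written, Table 4 lets a safety outcome decide who from one country is in its denominator. A China participant without an SAE can never be counted; one with an SAE can. Because no Day 1 sample is taken there, pre-existing immunoreactivity cannot be recognised, and any positive is classed as treatment-emergent. The baseline is missing by design, not by chance, and the SAP does not mention China anywhere in the ADA analysis.

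At stake are the meaning of the ADA denominator, the SAE frequency reported within that population, and the by-visit ADA summary. In a trial of about 75 participants per arm, one or two misplaced participants are visible in the tables.

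**Working it through.** The documents give no ADA rate, China enrolment or SAE rate, so there is no stated figure to reproduce. The check has a textual part and a sizing part.

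**Text: entry.** Table 4 needs one post-dose result. China has no scheduled samples, and its only route to a result is an SAE. So an SAE is necessary for entry. It is not sufficient: it must follow the first dose, and the sample must be obtained and give a result.

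**Text: windows.** SAP 5.4 restricts the windows for visit-based efficacy variables to scheduled measurements. The paragraph for pharmacokinetic and pharmacodynamic variables, whose Table 13 includes ADA, takes all available values without that restriction. The ADA windows have no gaps: after first dose to Day 126 is Week 12, Days 127 to 210 is Week 24, later is Week 36. A China SAE sample on Day 10 would stand as that participant's Week 12 result. If it were the only sample and positive, it would also be classed as indeterminate, since the last collected sample is the only positive one.

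**Size: inputs.** Dupilumab arm 75 (documents). Assumed: China share 5 to 30%, SAE risk s 2 to 10%, true ADA rate t 5 or 10%. Let n_C be China participants, n_O = 75 − n_C, and e = n_C × s the expected entrants. Then:

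- P(at least one entrant) = 1 − (1 − s)^n_C
- SAE frequency in the ADA population = (n_O × s + e)/(n_O + e)
- Incidence if entrants are positive with probability p = (n_O × t + e × p)/(n_O + e)

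| n_C / n_O | s | e | P(at least one) | SAE frequency | Incidence at t = 5%: p = 0 / 3t / 1 |
|---|---|---|---|---|---|
| 4 / 71 | 2% | 0.08 | 0.08 | 2.1% | 4.99 / 5.01 / 5.11% |
| 8 / 67 | 5% | 0.40 | 0.34 | 5.6% | 4.97 / 5.06 / 5.56% |
| 15 / 60 | 5% | 0.75 | 0.54 | 6.2% | 4.94 / 5.12 / 6.17% |
| 22 / 53 | 10% | 2.2 | 0.90 | 13.6% | 4.80 / 5.40 / 8.79% |

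The largest shift at p = 3t is in the last row with t = 10%: (53 × 0.10 + 2.2 × 0.30)/55.2 = 10.8%, or 0.8 points. The shift is e/(n_O + e) × (p − t). At t = 5%, reaching 1 point needs p = 0.05 + 0.01/(0.75/60.75) = 0.86 in the third row and 0.05 + 0.01/(2.2/55.2) = 0.30 in the fourth; the second row cannot reach it (0.4/67.4 × 0.95 = 0.56 points).

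These are expected values. One actual positive entrant moves 3/60 (5.0%) to 4/61 (6.6%); one negative entrant moves it to 3/61 (4.9%).

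**Direction.** A single sample finds less than three: at an assumed detection probability of 0.5 per sample in a truly positive participant, 0.5/(1 − 0.5^3) = 0.57 of what three would find. A missing baseline pulls the other way. The net sign is open.

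**ADA-safety link from China selection.** If the ADA-SAE relation is the same in China, entry through SAEs multiplies the cases in both ADA groups by the same factor, 75/n_O, and adds no non-cases. The odds ratio is unchanged. With assumed t = 8% and s = 5% in ADA-negatives, a risk ratio of 1.0 stays 1.0 (at a 20% share both risks rise from 5% to 6.2%). A risk ratio of 3.0 becomes 2.97, 2.93 or 2.88 at shares of 10, 20 or 30%, with the odds ratio at 3.35 throughout.

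**Event-triggered samples outside China.** With detection probability q per sample, detection is 1 − (1 − q)^n. Going from 3 to 4 or 5 samples changes it from 0.875 to 0.938 or 0.969 at q = 0.5 (7% or 11% more), by about 2% at q = 0.7 and by 0.1% at q = 0.9. The change is always upwards in participants with events, and only if the samples are assayed.

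**The case against.** SAP 4.8.2 opens with the scheduled time points and then lists the response classes, so a reader may take the classes to rest on scheduled samples. The unscheduled-visit rule in SAP 5.4 names laboratory data, vital signs and ECG, not ADA. Outside China, scheduled samples, including the end-of-treatment assessment at early discontinuation, will usually already qualify a participant, and the by-visit summary keeps the sample nearest the target day. The ADA-safety work is optional, safety analyses are descriptive, and ADA is outside the testing hierarchy. Dropping event-triggered positives from every summary could hide an ADA response found during an allergic reaction.

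Most of this stands and limits the consequence. It does not remove the gap for China, where the SAE sample is the only one, is collected for analysis, and meets the Table 4 rule.

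A reader might also infer that event-triggered samples elsewhere certainly count. The documents do not settle that: footnote f and Protocol 8.5.1.3 allow them to be merely archived, while Protocol 8.3 speaks of ADA assessment at onset and completion, if possible.

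Nor do they support a large detection effect. Independent 3% positivity per sample would give 1 − 0.97^n = 8.7%, 11.5% and 14.1% for 3, 4 and 5 samples, a ratio of 1.3 to 1.6. But ADA is a participant-level response, and the SAP itself defines persistent responses. On that footing the increase is 0.1% to 11%.

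**Conclusion.** The point holds as a gap in the population definition. Followed as written, China participants reach the treatment-emergent ADA denominator only through an SAE and without a baseline, and the SAE sample can be reported as a scheduled visit.

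The expected effect on incidence is small: within 0.8 points if entrants are positive up to three times as often as others, and above 1 point only where China enrolment, SAE risk and positivity among entrants are high together. Its direction is not fixed. SAE frequency in the ADA population is inflated, for example from an assumed 5% to between 5.3% and 6.9% over China shares of 5 to 30%. All shares, rates and detection probabilities are assumptions.

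A reader might conclude that ADA incidence and its link to safety events are biased by construction. The documents do not support that. China selection alone leaves a null association null, and the planned ADA-safety comparison may focus on injection site reactions, hypersensitivity and anaphylaxis, not on all SAEs. Extra sampling at events can pull towards a positive link, but modestly and only if those samples are assayed. The case for change is that it is cheap and removes outcome-dependent selection from a secondary endpoint's denominator.

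**What to change.** In SAP Table 4, define the ADA population as safety-population participants with at least one scheduled ADA result after the first dose. State that this leaves out China participants, and list their SAE-triggered results separately.

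In SAP 4.8.2, base the by-visit incidence and the optional ADA-safety comparison on scheduled samples. Alongside, report an any-sample count, so that positives found only in event-triggered samples are not hidden. The prespecified rule for a missing baseline can stay.

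The cost is SAP wording, one filter on sample type and one extra summary, with no new data. The denominator falls slightly against the current rule, by an expected 0.08 to 2.2 participants in the dupilumab arm under the assumptions above.

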9.3 POPULATIONS FOR ANALYSES

For purposes of analysis, the following populations are defined ([Table 5](#)):

Table 5 - Populations for analyses

Population	Description
Screened	All participants who sign the ICF.
Randomized	The randomized population includes all participants with a treatment kit number allocated and recorded in the IRT database, and regardless of whether the treatment kit was used or not. Participants treated without being randomized will not be considered randomized and will not be included in any efficacy population.
Intent-to-treat (ITT)	All randomized participants analyzed according to the treatment group allocated by randomization regardless if treatment kit is used or not
Efficacy	The analysis population for the efficacy endpoints will be the ITT population.
Safety	All participants randomly assigned to study intervention and who take at least 1 dose of study intervention. Participants will be analyzed according to the intervention they actually received. Randomized participants for whom it is unclear whether they took the study medication will be included in the safety population as randomized. For participants who accidentally receive different treatment from the planned, the actual intervention allocation for as-treated analysis will be the dupilumab group. The PD analyses will be performed on the safety population.
Pharmacokinetic (PK)	The PK population includes all participants in the safety population with at least one non-missing result for functional dupilumab concentration in serum after first dose of the study treatment. Participants will be analyzed according to the intervention actually received.
Antidrug antibody (ADA)	ADA population includes all participants in the safety population who have at least one non-missing ADA result after first dose of the study treatment. Participants will be analyzed according to the intervention actually received.

ADA: antidrug antibody; ICF: informed consent form; IRT: interactive response technology; ITT: intent to treat; PD: pharmacodynamics; PK: pharmacokinetic.

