4 STATISTICAL ANALYSES

4.1 GENERAL CONSIDERATIONS

In general, continuous data will be summarized using the number of observations available, mean, standard deviation (SD), median, minimum, and maximum. Categorical and ordinal data will be summarized using the count and percentage of participants.

The baseline value of efficacy parameters is defined as the last available value before randomization and prior to the first dose of study medication unless below eDiary data (WI-NRS, skin Pain-NRS and Sleep-NRS) score or otherwise specified.

The baseline for weekly average WI-NRS (skin Pain-NRS and Sleep-NRS) score is defined as the average of daily non-missing scores obtained during the 7 days prior to randomization.

The baseline value of the other parameters is defined as the last available value prior to the first dose of investigational medicinal product (IMP) if the participant is treated, or the last available value up to randomization if the participant is not exposed to IMP.

Observation period

The observation period will be divided into 4 segments:

- The **pre-treatment period** is defined as the period up to first IMP administration.
- The **treatment-emergent (TE) period** is defined as the period from the first IMP administration to the last IMP administration + 98 days. The treatment-emergent period includes the following 2 periods:
 - The **on-treatment period** is defined as the period from the first IMP administration to the last administration of the IMP + 14 days
 - The **residual treatment period** is defined as the period from the end of the on-treatment period to the end of the treatment-emergent period.
- The **post-treatment period** is defined as the period from the end of the treatment-emergent period.

The on-study observation period is defined as the time from start of intervention until the end of the study defined as the status date collected on e-CRF page “Completion of End of Study”.

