5.4 APPENDIX 4 DATA HANDLING CONVENTIONS

Demographic formulas

Age of onset of PN is calculated as:

$$\text{Year of PN diagnosis} - \text{Year of birth}$$

BMI is calculated as:

$$\text{Weight in kg} / (\text{height}^2 \text{ in meters})$$

Renal function formulas

For adults, creatinine clearance (CLcr) value will be derived using the equation of Cockcroft and Gault:

$$\text{CLcr (ml/min)} = (140 - \text{age}) \times \text{weight (kg)} \times \frac{(1 - 0.15 \times \text{sex (0-M, 1-F)})}{(\text{creatinine} \times (\mu\text{mol/l}))}$$

CLcr will be calculated using the last weight measurement on or before the visit of the creatinine measurement and age at the lab sampling day. Here age is calculated as following:

$$\text{Age} = \text{age collected at screening} + \text{integer part of (lab sampling analysis day/365.25)}$$

Analysis windows for time points

Efficacy assessment

For the efficacy assessment, the reference date for the derivation of relative days of events or findings will be the randomization day. If a participant receives IMP prior to the randomization by mistake, the reference date of efficacy assessment will be the date of the first IMP administration for that participant.

For daily eDiary data (WI-NRS, skin Pain-NRS, Sleep-NRS), all available values of daily measurements will be assigned to each week window according to [Table 10](#), and then weekly average score will be calculated. Randomization day is used as the reference day (Day 1).

Table 10 - Time window for eDiary efficacy variables

Time	Target day	Day range for calculating weekly score
Baseline (Week 0)	1	-7- <1
Week 1	8	1-11
Week 2	15	12-18
Week 3	22	19-25
Week 4	29	26-32
Week 5	36	33-39
Week 6	43	40-46
Week 7	50	47-53
Week 8	57	54-60
Week 9	64	61-67
Week 10	71	68-74
Week 11	78	75-81
Week 12	85	82-88
Week 13	92	89-95
Week 14	99	96-102
Week 15	106	103-109
Week 16	113	110-116
Week 17	120	117-123
Week 18	127	124-130
Week 19	134	131-137
Week 20	141	138-144
Week 21	148	145-151
Week 22	155	152-158
Week 23	162	159-165
Week 24	169	166-172
Week 25	176	173-179
Week 26	183	180-186
Week 27	190	187-193
Week 28	197	194-200
Week 29	204	201-207
Week 30	211	208-214
Week 31	218	215-221
Week 32	225	222-228
Week 33	232	229-235

Time	Target day	Day range for calculating weekly score
Week 34	239	236-242
Week 35	246	243-249
Week 36	253	250-256

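### The note below SAP Table 4 removes from every analysis population a participant dosed in error and then randomised, although Table 4 itself places that participant in ITT and Safety

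*SAP*

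**What the plan says.** SAP Section 3 defines the populations in Table 4 and then adds notes. In the table:

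- Randomized: "The randomized population includes all participants with a treatment kit number allocated and recorded in the interactive response technology (IRT) database". No condition is placed on when the first dose was given.
- Exclusion: "Participants treated without being randomized will not be considered randomized and will not be included in any efficacy population".
- ITT, which is also the Efficacy population: "All randomized participants analyzed according to the intervention group allocated by randomization regardless if treatment kit is used or not".
- Safety: anyone randomly assigned who took at least one dose.

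The first note below the table reads: "Participants exposed to study intervention before or without being randomized will not be considered randomized and will not be included in any analysis population". The sentence after it says that the safety experience of these participants will be reported separately.

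Protocol 6.3 defines a randomised participant by registration in the IRT. Protocol 9.3, Table 5 has the same narrow exclusion as SAP Table 4: "Participants treated without being randomized will not be considered randomized".

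SAP 5.4 (efficacy assessment) makes randomisation day the reference date, with one exception: "If a participant receives IMP prior to the randomization by mistake, the reference date of efficacy assessment" becomes the date of first IMP. The paragraph that introduces Table 10, for the daily diary scores, then gives randomisation day as Day 1 and states no exception. SAP 4.1 defines the weekly NRS baseline as the "average of daily non-missing scores obtained during the 7 days prior to randomization". For the other efficacy parameters, 4.1 requires a value that precedes both randomisation and the first dose.

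**The concern.** The note adds the words 'before or' to an exclusion that the table and the protocol limit to people who were never randomised. It also widens the exclusion from efficacy populations to all populations. The added words can only refer to people who were dosed and later randomised, because 'without' already covers the rest. Those people have an allocation, so removing them is an exclusion of randomised participants from the analysis labelled ITT, and it takes an exposed participant out of the safety denominators.

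Two programmers, one working from the table and one from the note, would build different primary populations if such a case occurred. The choice should be fixed before database lock, while it cannot be influenced by the outcome of the person concerned.

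**Working it through.** There is no planned figure to reproduce: the conflict is one of wording, and the response rates behind the sample size are redacted. The check follows one case through each rule: a participant receives IMP by mistake on one day and is allocated in the IRT *d* days later.

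| Rule | Test | Result |
|---|---|---|
| SAP Table 4, Randomized | Kit allocated and recorded in the IRT | In |
| SAP Table 4, ITT and Efficacy | All randomised participants | In |
| SAP Table 4, Safety | Randomly assigned, at least one dose | In |
| SAP Table 4 and Protocol Table 5, exclusion | Treated without being randomised | Does not apply |
| Protocol 6.3 | Registered by the IRT | Randomised |
| Note below SAP Table 4 | Exposed before or without being randomised | Out of every population |
| SAP 5.4, general efficacy rule | IMP before randomisation by mistake | Efficacy days counted from first IMP, which presumes that the data are analysed |

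**Size of one removal.** The inputs are 75 per arm (SAP 1.1) and an assumed response rate *p* of 20%, 40% or 60%, that is *x* = 15, 30 or 45 responders of 75. Removing one non-responder gives *x*/74, and removing one responder gives (*x* − 1)/74.

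| *x*/75 | Remove a non-responder | Remove a responder |
|---|---|---|
| 15/75 = 20.00% | 15/74 = 20.27% (+0.27) | 14/74 = 18.92% (−1.08) |
| 30/75 = 40.00% | 30/74 = 40.54% (+0.54) | 29/74 = 39.19% (−0.81) |
| 45/75 = 60.00% | 45/74 = 60.81% (+0.81) | 44/74 = 59.46% (−0.54) |

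The shift is therefore about 0.3 to 1.1 percentage points, in either direction. These are crude rates. The primary test is a stratified CMH test, so they show scale only.

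**Diary baseline (secondary).** Under SAP 4.1 the baseline week is the seven days before randomisation. With dosing *d* days earlier, up to *d* of those seven days (all seven once *d* reaches 7) fall after the first dose. With *d* = 0, a sequence error on the same day, none do. The day count for Table 10 depends on which part of 5.4 is followed:

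- Under the general exception, Day 1 is first IMP, and Table 10's baseline row is a different week from the one in 4.1.
- Under the diary sentence, Day 1 is randomisation. Table 10 and 4.1 then agree, but the baseline can contain post-dose scores.

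**The case against.** The strongest reply is that this will hardly ever matter. Allocation and kits come through the IRT (Protocol 6.3), and randomisation and first dose share Visit 2 in the schedule of activities. The triggering error also precedes allocation, so dropping the participant is unlikely to produce a large bias between arms. All of this stands. It limits the size of the point but leaves the contradiction in place, and the authors of 5.4 thought the case likely enough to write a rule for it.

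A reader might infer more than the documents support in five respects:

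- *That 5.4 expressly keeps the participant in ITT.* It sets a date for deriving relative days and says nothing about population membership. Retention is an implication, though a fair one, since an efficacy reference date has little use for someone in no efficacy analysis.
- *That the SAP replaced the protocol's definition.* Table 4 carries the protocol's exclusion unchanged. Only the note beneath it departs.
- *That safety information is lost.* Section 3 and SAP 4.7 both provide for separate reporting. What is lost is the place in the denominators.
- *That the same diary days are counted both as baseline and as Week 1.* This needs Table 10 to be anchored at first IMP while 4.1 stays at randomisation. The sentence introducing Table 10 keeps randomisation day as Day 1, so the overlap is not established. The documents show an unclear anchor and a baseline that may include post-dose days.
- *That each case moves the rate by 1/75 = 1.3 points.* That is the effect of one participant changing outcome with the denominator fixed. Removal also changes the denominator, which gives the smaller range above.

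**Conclusion.** The point holds as a contradiction within SAP Section 3, and between its note and the protocol. Followed literally, the note makes an exclusion from ITT and Safety that Table 4, Protocol 6.3 and Protocol Table 5 do not allow, and that SAP 5.4 appears not to expect. It is minor. The documents give no expected number of early-dosed participants, and that there would be few is an assumption based on the IRT process. One removal shifts an arm's rate by about 0.3 to 1.1 points, given 75 per arm and assumed response rates of 20% to 60%.

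The diary anchor is a secondary ambiguity. It affects the instrument of the primary endpoint, but only for a participant dosed at least a day before randomisation.

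**What to change.** In SAP Section 3, delete 'before or' from the note so that it matches Table 4. Add one sentence: any participant allocated in the IRT stays in ITT as allocated and, if dosed, in Safety, whatever the order of dosing and allocation. Separate safety reporting would remain for those never randomised.

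For the diary scores, choose one anchor for early-dosed participants and apply it together in the weekly baseline of 4.1, the diary sentence of 5.4 and Table 10. One workable choice is the earlier of randomisation and first IMP, for these participants only. Editing 4.1 alone would create a new gap: with Day 1 still at randomisation, the days between first IMP and randomisation would belong to neither baseline nor Week 1.

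The eligibility baseline in Protocol criterion I 03 should stay as it is. Its minimum of four scores in seven days applies to the week before randomisation, so the SAP should say what is done if the re-anchored week has fewer.

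The cost is a few sentences in the SAP before database lock. No new data are needed, because the diary runs daily from screening.
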